6.5.2.4 Adverse Events

Individual adverse events will be summarized as the number (%) of events and number and (%) of patients with the event in peanut ingestion and avoidance subjects. Adverse events will be modelled using Poisson regression and the rate of individual adverse events will compared between randomization arms through the desensitization DBPCFC visit. Long-term adverse events will be evaluated for those in the intervention group who are tested for sustained unresponsiveness following the desensitization DBPCFC visit. The Safety population will be used for this analysis.

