2) Ingestion of tolerated amounts of food, below a threshold of reaction, is generally safe and for those with high threshold peanut allergy, can be achieved using foods measured at home. The notion that allergens must be strictly avoided has come under scrutiny. In a series of studies conducted at Mount Sinai, children allergic to milk or egg but tolerant of baked forms were permitted to ingest these forms. The approach was noted to be safe, improved outcomes and is now a worldwide accepted approach. In these trials, children who incorporated baked milk had improved growth and caregiver-reported improvement in the quality of life compared to those who could have but did not incorporate the food, highlighting additional benefits of introducing tolerated amounts of food allergens to the diet. Indeed, there are other examples where persons with a food allergy are "permitted" to ingest a potential allergen with specific stipulations. OIT, currently under study in phase III trials, is another example of a change in approach where ingestion of a known allergen is permitted. OIT consists of introduction of the food allergen starting from minimal doses, usually in the subjects with exquisite allergy who react to a cumulative dose of 143 mg food protein or less (i.e., react at the single 100 mg dose given during a PRACTALL OFC). Following an initial dose escalation day, the dose of food is ingested daily and the treated subjects return every 2 weeks for dose escalations followed by a prolonged period of maintenance dosing. OIT, although often beneficial, carries a known adverse effect profile, with about 20% unable to progress. However, severe systemic reactions occur infrequently during OIT clinical trials; estimated rates of anaphylaxis are about 0.01% of all doses across various studies on peanut and milk OIT. Both severe and mild adverse events are more common during the initial dose escalation and in the early stages of build-up phase when dosing is being escalated from milligram doses every 2 weeks. Therefore, patients with high threshold food allergy as defined previously are anticipated to experience fewer reactions from being allowed to ingest sub-threshold amounts of the allergen, as we intend to study. In a study of 39 children with peanut allergy undergoing OIT aiming for a 4 gram maintenance dose, 26 who successfully attained this dose continued long term ingestion with few adverse events and no withdrawals. Their higher threshold therefore appears to be stable.

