# **3.1.4 Control Arm Procedures**

Children randomized to the control arm will follow standard care of strict avoidance of peanut. They will have a repeat DBPCFC to peanut at a time determined by a surveillance algorithm as described in Section 13.3, to match the distribution of DBPCFC to those of the intervention group. Based on the outcome of the DBPCFC, they will either be considered no longer allergic (naturally tolerant, NT) if they tolerate the full dose of the challenge (9043 mg) or will continue strict avoidance under clinical care off of the study.

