### AADCRC

regimens induce desensitization purposefully in an escalation phase rather than providing ingestion amounts known to be tolerated at presentation, and 3) permit dosing despite chronic symptoms. If extrapolation is accepted nonetheless, then the intervention (allowance of home ingestion of a tolerated amount) could be considered similar to the "maintenance phase" of peanut OIT. Most reactions to peanut OIT occur in the "escalation" or "build-up" phases. However, anaphylaxis rates are 0.01% across studies. In a representative study, the risk of dosing symptoms to peanut was 93% during the escalation day, 46% during build-up, but only 3.5% for final home dosing. Most of those symptoms were upper respiratory (1.2%), skin (1.1%) and abdominal (0.9%) with 0.3% affecting the chest (mild in 0.2%, moderate in 0.06%, none severe). These observations speak to the stability of a threshold even for those with a low peanut allergy threshold.

Having food allergy is a risk for eosinophilic esophagitis (EoE) and ingestion of ostensibly tolerated foods (i.e., no acute reaction) can be a trigger (most common triggers are milk and wheat). The risk that OIT can trigger EoE has been estimated at up to 2.7%. This risk will also be communicated to potential participants. Participants will be monitored for new onset of persistent gastrointestinal symptoms and or weight loss and if EoE is suspected they will be instructed to discuss this with their allergist or pediatrician for potential referral to a pediatric gastroenterologist for evaluation outside of the study, if necessary. Therapy will be stopped in case of new onset EoE; pre-existing EoE is an exclusion criterion.

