# 12.3 Grading and Attribution of Adverse Events

# 12.3.1 Grading Criteria

The study site will grade the severity of adverse events experienced by the study subjects according to the criteria set forth in the National Cancer Institute's Common Terminology Criteria for Adverse Events (NCI-CTCAE, 5.0), with the exception of anaphylaxis which will be graded according to the scale included in the definition section This document (referred to herein as the NCI-CTCAE manual) provides a common language to describe levels of severity, to analyze and interpret data, and to articulate the clinical significance of all adverse events. The NCI-CTCAE has been reviewed by the PI/Co-I and has been deemed appropriate for the subject population to be studied in this protocol.

Adverse events will be graded on a scale from 1 to 5 according to the following standards in the NCI-CTCAE manual:

Grade 1 = mild adverse event.

Grade 2 = moderate adverse event.

Grade 3 = severe and undesirable adverse event.

Grade 4 = life-threatening or disabling adverse event.

Grade 5 = death.

Only events grade 2 or higher and SAEs will be recorded on the appropriate AE case report form for this study.

For grading an abnormal value or result of a clinical or laboratory evaluation (including, but not limited to, a radiograph, an ultrasound, an electrocardiogram etc.), a treatment-emergent adverse event is defined as an increase in grade from baseline or from the last post-baseline value that doesn't meet grading criteria. Changes in grade from screening to baseline will also be recorded as adverse events, but are not treatment-emergent. If a specific event or result from a given clinical or laboratory evaluation is not included in the NCI-CTCAE manual, then an abnormal result would be considered an adverse event if changes in study therapy or monitoring are implemented as a result of the event. For additional information and a printable version of the NCI-CTCAE manual, consult the NCI-CTCAE web site: http://ctep.cancer.gov/reporting/ctc.html.

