# **13.4.4** Analyses of Secondary and Other Endpoint(s)/Outcome(s)

*Sustained unresponsiveness or natural tolerance*: The proportion of children who experience SU in the active arm of the HT group will be compared to the proportion of children who achieve natural tolerance in the control arm in an intent-to-treat analysis using a continuity corrected chi-squared test, similar to the plan detailed for the primary endpoint.

*Immunological parameters*: Changes in skin prick test mean wheal diameter will be compared between randomization groups using linear mixed effects models for data collected at baseline and desensitization DBPCFC. The linear mixed effects model has the advantage that the estimation of the model parameters will be unbiased even in the presence of missing outcomes, assuming that the missing values depend only on the observed values (MAR). If the MAR assumption is not plausible, pattern-mixture modeling (which stratifies subjects by their pattern of missing data) will be used.

**Quality of life**: Changes in quality of life over the study as measured by The Food Allergy Quality of Life-Parental Burden will be compared between randomization groups and analyzed using linear mixed effects models as described previously (Immunological parameters, above).

**Adverse Events**: Adverse events (AEs) will be coded using the CTCAE, Common Terminology Criteria for AE, V4.0. Individual adverse events will be summarized as the number (%) of events and number (%) of patients with the event in each group. Adverse events will be modelled using Poisson regression and the rate of individual adverse events will compared between randomization arms over the study period. **Long-term adverse events** will be evaluated with data up to 96 weeks for those in the active group who are tested for SU following a desensitization DBPCFC.

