We do not anticipate many families becoming "drop-in" doing this because those randomized to avoidance will not have their tolerance of a specific measured amount confirmed under supervision and there is generally a concern of allergic reactions from ingestion. More importantly, we believe this concern will be easily addressed because there are true issues of equipoise. It may be that those randomized to ingestion will have more allergic reactions than controls, or develop side effects such as eosinophilic esophagitis, or not be able to progress on the large steps outlined in the PRACTALL modified dosing. If families on avoidance are non-adherent, we can detect this. We will monitor peanut-specific IgG levels in all participants and those with rising peanut-specific IgG from ingestion could be identified. The statistical analysis plan includes a sensitivity analysis that uses instrumental variable methods to obtain an unbiased estimate of the treatment effect in the presence of cross-overs.

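### Adverse-event rates are compared by Poisson regression with no allowance for children differing in proneness, so intervals are too narrow for event types that recur in both arms

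*SAP*

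**What the plan says.** SAP 6.5.2.4 summarizes each adverse event by number of events and number of children, then adds that "Adverse events will be modelled using Poisson regression and the rate of individual adverse events will compared between randomization arms", up to the desensitization challenge. Protocol 13.4.4 has the matching sentence: "Adverse events will be modelled using Poisson regression and the rate of individual adverse events will compared between randomization arms over the study period". Neither text names a robust variance, a dispersion parameter, a subject effect or an offset. By contrast, the SAP does name a random subject effect for skin prick test (6.5.2.2) and quality of life (6.5.2.3).

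Four other places bear on the point:

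- **Expected direction.** Protocol 13.7 concedes: "It may be that those randomized to ingestion will have more allergic reactions than controls". In the other arm, "Children randomized to the control arm will follow standard care of strict avoidance of peanut" (protocol 3.1.4).
- **Recording threshold.** "Only events grade 2 or higher and SAEs will be recorded on the appropriate AE case report form for this study" (protocol 12.3.1).
- **General fallback.** SAP 6.1 allows an unsuitable method to be replaced, including by another modeling technique. It sets no dispersion check, trigger or replacement.
- **Status.** SAP 6.6 makes secondary p-values descriptive.

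**The concern.** Poisson standard errors assume that, apart from follow-up time, all children in an arm share one underlying event rate. Repeated events in a child do no harm by themselves. The trouble comes when some children are persistently more prone than others: the variance of the counts then exceeds their mean, and the model does not see the excess.

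Differing proneness is plausible here. Baseline cumulative reaction doses run from 443 to 5043 mg (SAP 3.1.2), and eligible peanut IgE runs from above 0.35 to 50 kUA/L (protocol 4.2 and 4.3).

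Safety is a named secondary endpoint (SAP 5.2), and this is the only planned between-arm model of adverse-event rates. What is at stake is how precise the rate ratios in the safety table appear to be.

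**Working it through.** **Is there a figure to reproduce?** Not for this comparison: the documents give no event rate, precision or power for adverse events. The only stated power is about 85% for the primary endpoint with 36 per arm. It reproduces (84.2% by the continuity-corrected approximation, 85.9% by exact enumeration), so 36 per arm is used below.

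**Formula.** Let m1 and m0 be mean events per child (ingestion, avoidance), n the children per arm, and k the variance of a gamma-distributed proneness factor with mean 1.

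- Poisson variance of the log rate ratio: (1/m1 + 1/m0)/n
- Actual variance: (1/m1 + 1/m0 + 2k)/n
- Factor by which the Poisson standard error is too small: sqrt(1 + 2k/(1/m1 + 1/m0))

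Example with m1 = 1, m0 = 0.5, k = 1: the Poisson variance is 3/36 = 0.083 and the actual variance is 5/36 = 0.139, so the factor is sqrt(5/3) = 1.29. The smaller mean dominates 1/m1 + 1/m0, so the arm with fewer events largely sets the size.

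**Simulation.** 40,000 trials per cell, 36 per arm, gamma-Poisson counts, the same k in both arms and equal follow-up. The means and k are assumptions. Entries are for k = 0.5 / 1 / 2.

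| Events per child, ingestion vs avoidance | Standard-error factor | Non-coverage of nominal 95% Poisson interval |
|---|---|---|
| 1 vs 0.5 | 1.15 / 1.29 / 1.53 | 8.3 / 12.1 / 19.0% |
| 1 vs 0.25 | 1.10 / 1.18 / 1.34 | 6.2 / 8.4 / 12.9% |
| 0.5 vs 0.25 | 1.08 / 1.15 / 1.29 | 5.6 / 7.2 / 11.0% |
| 0.5 vs 0.5 | 1.12 / 1.22 / 1.41 | 7.4 / 10.3 / 15.3% |
| 1 vs 0.1 | 1.04 / 1.09 / 1.17 | 4.0 / 4.9 / 6.2% |
| 0.5 vs 0.1 | 1.04 / 1.08 / 1.15 | 4.1 / 4.9 / 6.2% |

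With k = 0, non-coverage in the unequal-mean rows lies between 3.4 and 4.7%, so nothing is inflated without differing proneness. At an avoidance mean of 0.1 the interval starts out conservative, which absorbs most of the effect; trials with an empty arm (at most 4%) were excluded there. Follow-up of 32, 56, 64 or 72 weeks with an offset changes the unequal-mean figures by less than 1 point. Sandwich variance gives 3.3 to 6.6% in the unequal-mean cells.

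**Which means are plausible?** The model is for individual adverse events, read here as each event type separately. Protocol 5.2 cites an oral immunotherapy study with dosing-symptom rates of "46% during build-up, but only 3.5% for final home dosing". By type, home dosing gave 1.2% upper respiratory, 1.1% skin and 0.9% abdominal, with "0.3% affecting the chest (mild in 0.2%, moderate in 0.06%, none severe". One dose a day for 32 to 72 weeks is 224 to 504 doses.

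| Type | Symptoms per child | Share that must be grade 2 or higher for a mean of 2 |
|---|---|---|
| Upper respiratory | 2.69 to 6.05 | 33 to 74% |
| Skin | 2.46 to 5.54 | 36 to 81% |
| Abdominal | 2.02 to 4.54 | 44 to 99% |
| Chest | 0.67 to 1.51 | cannot reach 2 |

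The only graded split is for chest: 0.06/0.3 = 20% moderate. If 20% also held for the other three types (an assumption), their ingestion means would be about 0.4 to 1.2, hence the rows at 0.5 and 1. For anaphylaxis, protocol 1.2 says "estimated rates of anaphylaxis are about 0.01% of all doses across various studies on peanut and milk OIT": 0.0001 × 224 to 504 is 0.02 to 0.05 per child, too rare for this to matter. Protocol 5.2 itself warns that extrapolation from oral immunotherapy may not apply.

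**The case against.** The strongest reply is that the effect is close to nil where it would matter most. The avoidance arm governs the size, only grade 2 or higher events go on the form, and no text supports an avoidance mean of 0.25 or more for one event type. At 0.1 the Poisson interval is near nominal, and the sandwich interval (3.3 to 3.7%) is slightly conservative. This stands for allergic reactions, with one reservation: protocol 6.3 wants all allergic reactions reported, and the SAP does not say which source feeds the model, so higher counts cannot be excluded. It does not cover event types that also occur in avoiders.

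The protocol also curbs recurrence, since 8.4 provides for reducing or stopping ingestion after moderate or severe symptoms. A constant-rate simulation ignores this, and the range for k is assumed. Both are fair, and they are why the size is given only as a range.

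The texts do not actually say that model-based variance will be used, SAP 6.1 permits another technique, and SAP 6.6 calls the p-values descriptive. These soften the point. They do not widen an interval that is too narrow, and a switch under 6.1 would be chosen after seeing the data.

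A reader might infer much larger errors, such as 16, 26 and 38% at two events per child in both arms, or reach a mean of 2 from the pooled 3.5% rate. The documents do not support this: the model is by event type, and the per-type rates above make a mean of 2 unlikely or impossible. Nor is this the only between-arm safety model, because SAP 6.5.3.1 compares severity scores during food challenges, as an exploratory analysis.

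**Conclusion.** The concern holds in a conditional form and is minor. If proneness varies between children, the planned intervals are too narrow for event types that recur in both arms: non-coverage is roughly 6 to 19% over the cells with avoidance means of 0.25 to 0.5 and k from 0.5 to 2. At an avoidance mean near 0.1 it is about 4 to 7%, and with no variation in proneness there is no inflation. The event means and k are assumptions, because the documents supply neither.

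It would go too far to conclude that the safety comparison as a whole is unreliable. Rare event types are hardly touched, the number of children with each event is reported and unaffected, and the suspension triggers in protocol 11.5 are counts of deaths or subjects, not modelled rates. The primary analysis and the sample size do not depend on this model.

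**What to change.** In SAP 6.5.2.4, prespecify Poisson regression with sandwich variance by child, or negative binomial regression, and state log follow-up time as the offset. Comparing rates already implies an offset, and planned follow-up runs from about 32 to 72 weeks. For rare event types, compare the number of children with at least one event by an exact test; that count is already in the planned summary.

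The cost is one or two sentences and one software option, and the SAP allows revision before data lock. The downsides are slightly wider intervals for recurrent events, slight small-sample inflation of the sandwich interval (non-coverage up to about 6.6%), and a conservative exact test (it rejects 0.2 to 2.8% of the time under no difference at means of 0.05 to 0.25).

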### 2.3. Secondary Objective(s)

### Secondary clinical objectives

The secondary clinical objectives of this study are to determine whether ingesting sub-threshold amounts of peanut in children with high threshold peanut allergy, compared to avoidance, will:

- A) Result in increased rates of sustained unresponsiveness.
- B) Have positive effects on quality of life.
- C) Be a safe approach.

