### AADCRC

Those discontinuing peanut for the above reasons will continue with other study procedures (e.g., monthly calls, AE monitoring, SU DBPCFC).

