### 12.2 Definitions

### 12.2.1 Adverse Event (AE)

Any untoward or unfavorable medical occurrence associated with the subject's participation in the research, whether or not considered related to the subject's participation in the research (modified from the definition of adverse events in the 1996 International Conference on Harmonization E-6 Guidelines for Good Clinical Practice) (from OHRP "Guidance on Reviewing and Reporting Unanticipated Problems Involving Risks to Subjects or Others and Adverse Events (1/15/07)" http://www.hhs.gov/ohrp/policy/advevntguid.html#Q2)

For this study, any adverse event will be assessed for relationship during the following times frames with:

- **Study therapy regimen**: Ingestion of sub-threshold amounts of home-measured, home-purchased peanut. AEs will be collected until study completion or withdrawal.
- **Study mandated procedures**: AEs associated with DBPCFC, blood draw, observed feedings, skin prick tests will be monitored for 24 hours after the procedure.

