# **12.3.2** Attribution Definitions

The relationship, or attribution, of an adverse event to the study therapy regimen or study procedure(s) will initially be determined by the site investigator or Sponsor-investigator and recorded on the appropriate AE eCRF. Final determination of attribution for safety reporting will be determined by the Sponsor-Investigator. The relationship of an adverse event to study therapy regimen or procedures will be determined using the descriptors and definitions provided in Table 12.3.2.

Code	Descriptor	Relationship (to primary investigational product and/or other concurrent mandated study therapy or study procedure)			
UNRELATED CATEGORY					
1	Unrelated	The adverse event is clearly not related: there is insufficient evidence to suggest a causal relationship.			
RELATED CATEGO	RELATED CATEGORIES				
2	Possible	The adverse event has a reasonable possibility to be related; there is evidence to suggest a causal relationship.			
3	Definite	The adverse event is clearly related.			

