2.2 Secondary Clinical Objectives

The secondary clinical objectives include assessing the development of sustained unresponsiveness (a surrogate term for tolerance without daily ingestion), effects on quality of life, changes in skin prick test mean wheal diameter and safety in participants randomized to peanut ingestion compared to avoidance.

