4. ANALYSIS POPULATIONS

Four populations will be used for all summaries and analyses.

Screened Population

The screened population will consist of all subjects who signed a consent form and met enrollment eligibility prior to the baseline DBPCFC.

Intent-to-Treat (ITT) Population

The ITT population will consist of all randomized subjects grouped by their assignment at randomization whether or not they actually received the treatment to which they were assigned. This sample will be used for summaries and analyses of the primary and secondary (where applicable) clinical endpoints. The ITT population will be used for the primary and secondary (where applicable) analyses and description of patient and baseline characteristics.

All Available Data Population

The All Available Data population will consist of randomized subjects with at least one longitudinal assessment of the secondary clinical endpoint (e.g., Quality of Life). Subjects will be analyzed in the group they were randomized. The All Available Data population will be identical to the ITT population if all randomized subjects have at least one measurement.

Per Protocol Population

The Per Protocol Population will consist of subjects in the intervention group who attended two-thirds of the updosing visits and the desensitization DBPCFC visit and subjects in the control group who did not consume peanut based on IgG 4 levels.

Safety Population

The Safety population will consist of all randomized subjects in the intervention group who received any amount of peanut after the baseline DBPCFC and all randomized subjects in the control group. The Safety population will be identical to the ITT population if all randomized subjects in the intervention group receive the assigned treatment. The Safety population will be used for the analysis of safety data.

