6.3 Crossover

Crossovers are subjects who after randomization switch from the allocated treatment to the non-allocated treatment. Subjects randomized to peanut ingestion who never consume peanut after the baseline DBPCFC or who permanently discontinue peanut consumption will be considered crossovers. In addition, subjects randomized to avoidance who start ingesting peanut and continue consumption through the desensitization DBPCFC visit (or study discontinuation, whichever comes first) will be considered to have crossed over. Should crossover occur, crossovers will be analyzed as belonging to the group to which they were randomized according to the ITT principle in all efficacy analyses. Safety analyses will be conducted according to the definition of the Safety population described in section 4.

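### Adverse-event rates are compared by arm through the endpoint food challenge, so reactions the challenge provokes, expected more often in controls, dilute the safety ratio; they should be tabulated separately

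*SAP*

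**What the plan says.** SAP 6.5.2.4 summarises each adverse event as a count of events and of patients. It then fits a Poisson regression in which "the rate of individual adverse events will compared between randomization arms through the desensitization DBPCFC visit". The analysis uses the Safety population, defined in SAP 4 as "all randomized subjects in the intervention group who received any amount of peanut after the baseline DBPCFC and all randomized subjects in the control group". No person-time offset is named.

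Protocol 12.2.1 brings challenge reactions into AE collection: "AEs associated with DBPCFC, blood draw, observed feedings, skin prick tests will be monitored for 24 hours after the procedure". Protocol 12.3.2 records whether an event is related to the study regimen or to a procedure, but SAP 6.5.2.4 does not use that information. Protocol 12.3.1 limits the AE form to events of grade 2 or higher and serious events.

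SAP 5.2 lists acute allergic reactions (including anaphylaxis) and gastrointestinal side effects as the safety parameters. SAP 2.2 states the safety objective as "safety in participants randomized to peanut ingestion compared to avoidance".

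**The concern.** The challenge at the end of the comparison window is the efficacy measurement. It raises the dose until the child reacts or reaches 9043 mg, so it is designed to produce the events that the safety endpoint counts. Both arms undergo it. If the intervention works, fewer intervention children react there. The safety rate then contains a component that reflects efficacy, and that component favours the intervention.

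At stake is the estimated excess of allergic reactions from daily peanut. Families and allergists need the excess that arises from eating peanut at home and at up-dosing visits. A ratio mixed with challenge reactions understates it. The patient counts are affected too, because most control children could appear as having had an allergic reaction that only the trial's own test produced.

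**Working it through.** **Reproducing the plan's rates (SAP 6.5.1.1).** Inputs are 55% and 10% success, 20% drop-out, 5% drop-in and 36 children per arm.

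- Intervention: 0.80 × 0.55 + 0.20 × 0.10 = 0.46.
- Control: 0.95 × 0.10 + 0.05 × 0.55 = 0.1225.
- Difference: 0.3375. All three agree with the plan.

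**From success rates to challenge reactions.** A child who completes the challenge and misses the endpoint is taken to have reacted before 9043 mg.

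- Intervention: 1 − 0.46 = 0.54, or 0.54 × 36 = 19.4 children.
- Control: 1 − 0.1225 = 0.8775, or 0.8775 × 36 = 31.6 children.

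If every child is challenged, these are minimum values, because a child who gains two steps but does not reach 9043 mg succeeds and still reacts.

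**Effect on the rate ratio.** Let b be the other events per control child and R the true by-arm ratio for those events. Follow-up is taken as equal, which the control-timing algorithm aims for, with one event per reacting child. The reported ratio is (R × b + 0.54) / (b + 0.8775). The documents give no AE rates, so b and R are assumptions.

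| True R | b = 0.5 | b = 1 | b = 2 |
|---|---|---|---|
| 3 | 2.04/1.3775 = 1.48 | 3.54/1.8775 = 1.89 | 6.54/2.8775 = 2.27 |
| 2 | 1.54/1.3775 = 1.12 | 2.54/1.8775 = 1.35 | 4.54/2.8775 = 1.58 |
| 1 | 1.04/1.3775 = 0.75 | 1.54/1.8775 = 0.82 | 2.54/2.8775 = 0.88 |

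**When the ratio reads below 1.** This happens when b × (R − 1) is less than 0.8775 − 0.54 = 0.3375, which is the planned efficacy difference. The threshold is R below about 1.68, 1.34 and 1.17 for b = 0.5, 1 and 2.

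**Sensitivity.**

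- Equal challenge risk of 0.9 in both arms: a true 3 reads 2.4/1.4 = 1.71, 3.9/1.9 = 2.05 and 6.9/2.9 = 2.38 for b = 0.5, 1 and 2. A true 1 stays at 1.
- Equal risk of 0.5 with b = 1: 3.5/1.5 = 2.33.
- Only half of challenge reactions recorded (0.27 and 0.43875) with b = 1: a true 3 reads 3.27/1.43875 = 2.27, and a true 2 reads 2.27/1.43875 = 1.58.

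The model is fitted to individual event types. These figures therefore apply to the types a challenge provokes (skin, respiratory, gastrointestinal and anaphylaxis), not to unrelated events.

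**The case against.** The strongest defence is that the by-arm comparison answers the SAP's own safety objective, that secondary p-values are descriptive (SAP 6.6), and that SAP 6.1 already permits additional analyses. SAP 6.5.3.1 also compares the severity of challenge reactions between arms. Recording only grade 2 or higher events will keep some challenge reactions out. All of this is true and limits the stakes. But the severity analysis does not remove challenge events from the rate, and a post hoc separation is weaker than one fixed before data lock.

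It could also be said that the shift would be lost in noise at this size. With b = 1 and R = 3, 36 control and 108 intervention events give a 95% Poisson interval of exp(ln 3 ± 1.96 × √(1/36 + 1/108)), or 2.06 to 4.37. The reading of 1.89 lies outside that interval, so the bias is not negligible under that assumption.

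A reader might go further and infer that a comparison by assignment is itself wrong, and that the plan must estimate the rate while a child is eating peanut. The protocol's secondary clinical objectives do speak of "ingesting sub-threshold amounts of peanut in children with high threshold peanut allergy, compared to avoidance". Children who stop peanut do remain under AE monitoring (Protocol 6.5). The documents still do not support that reading. The same opening phrase covers sustained unresponsiveness and quality of life, which are also analysed by arm. The safety item asks about an approach, and SAP 2.2 frames safety by assignment.

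The dilution from off-peanut time is also modest. As an illustration, take 5.4 stoppers (15% of 36) at week 16, half followed to week 72 and half for 30/7 = 4.29 weeks. Off-peanut time is 5.4 × (0.5 × 56 + 0.5 × 4.29) = 162.8 child-weeks. With the other 30.6 children at a mean of 56 or 72 weeks, total time is 1962.8 or 2452.4, a share of 8.3% or 6.6%. A true 3 then reads 1 + 2 × (1 − share) = 2.83 or 2.87. Censoring when a child stops because of reactions is informative, so such a rate could only be descriptive.

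**Conclusion.** The point holds for challenge reactions. As written, the safety rate includes reactions provoked by the efficacy test, and the plan's own assumptions imply more of them in controls. A true ratio of 3 would read about 1.5 to 2.3 and a true 2 about 1.1 to 1.6. Ratios near 1 could read below 1.

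This rests on 0.5 to 2 other events per control child, equal follow-up, one recorded event per reacting child, and challenge reactions at the minimum values implied by SAP 6.5.1.1. It shrinks if many reactions are below grade 2. If the two arms react equally often, a true 1 is unbiased, but larger ratios are still pulled toward 1.

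The documents do not show that the trial's safety conclusion will be wrong, since they give no event rates. They also do not show that analysis by assignment should be replaced. The priority is modest, but the correction is nearly free.

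**What to change.** In SAP 6.5.2.4, before data lock:

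- Keep the Poisson comparison by randomised arm in the Safety population, and name log person-time as the offset.
- Exclude events attributed to a DBPCFC from the main rate and from the patient counts beside it. Use the attribution recorded under Protocol 12.3.2. If the coding does not identify the procedure, use onset within 24 hours of a DBPCFC, the window in Protocol 12.2.1.
- Tabulate DBPCFC events separately by arm.
- Keep reactions at supervised up-dosing feedings in the intervention rate, because they are part of the intervention. Show them on their own line beside home-dose reactions.
- Report the all-events rate as well, so that nothing is hidden by the exclusion.

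The cost is one SAP paragraph and one extra table from data already collected. The drawback is reliance on attribution coding, made by investigators who know the assignment; the 24-hour rule may also remove an occasional unrelated event. An on-peanut person-time rate may be added, but it is optional and should be labelled descriptive.
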